16.3 Other Endpoint Analyses

16.3.1 Analysis of PK Endpoints

Predose samples that occur before the first drug administration will be assigned a time of 0 hours, as if the sample had been taken simultaneously with the study drug administration.

Pharmacokinetic concentrations which are erroneous due to a protocol deviation (as defined in the protocol), documented handling error or analytical error (as documented in the bioanalytical report) may be excluded from the PK analysis if agreed upon prior to performing a statistical analysis. In this case, the rationale for exclusion must be provided in the Clinical Study Report (CSR). Any other PK concentrations that appear implausible to the Pharmacokineticist must not be excluded from the analysis. Any implausible data will be documented in the CSR.

All statistical analyses and descriptive summaries of PK data will be performed on the PK Population. Pharmacokinetic concentrations will be listed for all subjects by treatment and fed/faasted group; concentrations excluded from the PK analysis will be flagged within the listing.

A listing of PK blood sample collection times by individual, as well as derived actual sampling time and time deviations, will be provided.

Plasma concentration data will be summarized descriptively for metformin as described in Section 10. Values below the LLOQ will be taken as zero for descriptive statistics of PK concentrations. Missing concentrations (e.g., no sample, insufficient sample volume for analysis, no result, or result not valid) will be reported and displayed generally as “N.R.”.

Samples that are collected outside the specified time windows will be included in the PK analysis but excluded from the concentration summary. The PK sampling collection schedule is presented in Table 8 below.

Table 8 Pharmacokinetic Sample Collection Schedule

Trial Day	Period Day	Time of Blood Sample (hour)	Window Allowance (minute)
1	1 - Predose in Period 1	Baseline blood draw (10 minutes prior to drug administration)	±2
1	1 – Single dose administration	0.5, 1, 2, 3, 4, 5, 6, 7, 8, 10, 12, 14	±2
2	2	24, 30, 36	±5
3	3	48	±5
4 – 7 (wash-out)	NA	NA	NA
8	1-Predose in Period 2	Baseline blood draw (10 minutes prior to drug administration)	±2
8	1 – Single dose administration	0.5, 1, 2, 3, 4, 5, 6, 7, 8, 10, 12, 14	±2
9	2	24, 30, 36	±5
10	3	48	±5
End of Trial (Day 15)/ Premature Withdrawal		1-sample	±30

Individual concentration-time profiles showing all subjects by treatment and fed/fasted group (i.e., individual subject overlay plots), and/or showing all treatment groups by subject (i.e., by-subject plots) will be created using the actual time points and the numeric concentration data. Arithmetic mean concentration-time profiles by treatment and fed/fasted group will be provided using scheduled (nominal) time points and the numeric concentration data. All concentration-time plots for PK data will be presented both on a linear and on a semi-logarithmic scale. Mean plots will include SD error bars when plotted on a linear scale.

16.3.2 Estimation of Individual Pharmacokinetic Parameters by Noncompartmental Analysis

For the PK analysis, predose sample concentrations that are below the LLOQ or that are missing will be assigned a numerical value of zero for the calculation of AUC. Any anomalous concentration values observed at predose will be identified in the CSR, and if the anomalous predose concentration value is greater than 5.00% of the C_{max} in the profile, the profile will be included in the PK analysis, but the concentration data and the corresponding derived PK parameters will be excluded from summaries and inferential statistics as appropriate; handling of the data will be documented in the CSR.

Pharmacokinetic parameters will be calculated using standard noncompartmental methods (calculation method: linear up log down) and the actual administered dose. Pharmacokinetic parameters will be calculated and listed for all volunteers who provide sufficient concentration-time data. At least 3 valid, postdose concentration points will be required in the PK profile to obtain any PK parameter estimate.

Pharmacokinetic parameters will be calculated using the actual elapsed time since dosing, given with a precision of 14 significant digits or the SAS format Best12. In cases where the actual sampling time is missing, calculations will be performed using the scheduled time. Otherwise, there will be no further imputation of missing data other than for a missing predose concentration as stated above.

For each subject in the PK Population the following PK parameters will be calculated for metformin, where appropriate:

Symbol	Definition
AUC _{0→t}	The AUC from time zero (= dosing time) to the time the last concentration is at or above the LLOQ (t _{last}). Calculated using the mixed log linear trapezoidal rule (linear up, log down). Units: ng*h/mL.
AUC _{0→∞}	The AUC from time zero (= dosing time) extrapolated to infinity, based on the predicted value for the concentration at t _{last} , as estimated using the linear regression from λ _z determination. AUC _{0→∞} = AUC _{0→t} + C _{last pred} / λ _z . Units: ng*h/mL. The predicted AUC _{0→∞} will be reported.
AUC _{extra%}	The AUC from time t _{last} extrapolated to infinity given as percentage of AUC _{0→∞} . AUC _{extra%} = (extrapolated area/AUC _{0→∞}) *100. The predicted AUC _{0→∞} will be used. Units: %.
CL _f	The apparent total body clearance of drug following extravascular administration, taking into account the fraction of dose absorbed. CL _f = Dose _{p.o.} /AUC _{0→∞} . The predicted AUC _{0→∞} will be used. The dose amount to be used for this calculation is 500 mg. Units: L/h.
C _{max}	Maximum observed concentration, taken directly from the observed concentration-time profile. Units: ng/mL.
t _{max}	The time to reach the maximum observed concentration (unless otherwise defined, take the first occurrence in case of multiple/identical C _{max} values). Units: h.
t _{1/2}	Apparent terminal half-life. t _{1/2} = ln (2)/λ _z . Units: h.
V _{z/f}	The apparent volume of distribution during the terminal phase following extravascular administration, based on the fraction of dose absorbed. V _{z/f} = Dose/*AUC _{0→∞} *λ _z) following single dose. The predicted AUC _{0→∞} will be used. Units: L.

λ_z	Terminal elimination rate constant. Determined from the terminal slope of the log-transformed concentration curve using linear regression on terminal data points of the curve. Units: h^{-1} .
-------------	--

The predicted $\text{AUC}_{0 \rightarrow \infty}$ will be reported and used in the determination of other parameter estimates, i.e., $\text{AUC}_{\text{extra}\%}$, CL/f , and $\text{V}_{\text{z/f}}$. The following PK parameters will be calculated for diagnostic purposes and listed, but will not be summarized:

- The time interval (h) of the log-linear regression (λ_z lower, λ_z upper) to determine λ_z .
- Number of data points (N_λ) included in the log-linear regression analysis to determine λ_z .
- Goodness-of-fit statistic (Rsq) for calculation of λ_z .

The regression analysis should contain data from at least 3 different time points in the terminal phase consistent with the assessment of a straight line on the log-transformed scale. Phoenix WinNonlin best fit methodology will be used as standard. The last quantifiable concentration should always be included in the regression analysis, while the concentration at t_{max} and any concentrations below the LLOQ which occur after the last quantifiable data point should not be used.

The Rsq should be ≥ 0.800 and the observation period over which the regression line is estimated should be at least two-fold the resulting $t_{1/2}$ itself. If these criteria are not met, then the rate constants and all derived parameters (e.g., $\text{AUC}_{0 \rightarrow \infty}$, $\text{AUC}_{\text{extra}\%}$, CL/f , $t_{1/2}$, and $\text{V}_{\text{z/f}}$) will be included in the parameter outputs and descriptive statistics but will be flagged and discussed appropriately. Any flags should be included in the study specific SDTM.

To ensure a reliable estimate of the extent of exposure in pivotal trials (e.g., BE), $\text{AUC}_{\text{extra}\%}$ should be less than or equal to 20.0%. If $\text{AUC}_{\text{extra}\%}$ is greater than 20.0%, all parameters derived using λ_z (i.e., $\text{AUC}_{0 \rightarrow \infty}$, $\text{AUC}_{\text{extra}\%}$, λ_z , $t_{1/2}$, $\text{V}_{\text{z/f}}$, and CL/f) will not be included in the calculation of descriptive statistics or statistical analyses.

The dose amount for IMP administered is that of the active, free drug substance only, and is synonymous with the measured analyte. No adjustment for the dose amount value of IMP will be applied when 'dose' is used in calculating PK parameters with formulas needing a dose value.

The Phoenix WinNonlin NCA Core Output will be provided in a separate listing.

17 Safety Evaluation

The subsections in this section include specifications for summarizing safety endpoints that are common across clinical trials such as adverse events, laboratory tests, ECG recordings and vital signs. Safety analyses will be done on the Safety Population. All safety data will be listed in individual subject listings by group, treatment sequence and subject.

All safety variables will be analyzed using descriptive statistics. For the evaluation of safety parameters, the continuous variables will be summarized descriptively by N, mean, median, SD, Q1-Q3, and minimum and maximum values.

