9.3 Populations for Analyses

The analysis populations are specified below. The final decision to exclude participants from any analysis population will be made prior to database lock.

Analysis Population	Description
Screening Population	The Screening Population includes all subjects who have signed the main informed consent (i.e., screening failures plus subjects enrolled).
Safety Population	The Safety Population includes all participants who received at least 1 dose of IMP. In general, clinical data will be analyzed for the Safety Population.
Pharmacokinetic Population	The PK Population includes all participants who completed the study with adequate study medication compliance, without any relevant protocol violations or events with respect to factors likely to affect the comparability of PK results, and with sufficient evaluable data to determine primary endpoints (AUC_{0-t} and C_{max}) for both treatments. If participants receive concomitant medication that potentially affects PK for the treatment of an AE, their inclusion in the PK Population will be decided on a case-by-case basis. Emesis occurring within 2 times of the median t_{max} for a given treatment will be considered a relevant event likely to affect the comparability of PK results. Similarly, a predose concentration for a given treatment period that exceeds 5% of C_{max} will be considered a relevant event affecting PK results. All PK analyses will be based on the PK Population. Data for subjects excluded from the PK Population will be included in listings.

PK = pharmacokinetic.

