10.1 Definition of Protocol Deviations

Protocol deviations describe how close the study has been conducted according to the protocol as expected per GCP. Some of these deviations may be significant contributors to analysis bias.

Important protocol deviations are protocol deviations that might significantly affect the completeness, accuracy, and/or reliability of the study data or that might significantly affect a subject's rights, safety, or well-being.

Examples of clinically important protocol deviations or important events for PK include, but may not be limited to, the following:

- Subjects that are dosed on the study despite not satisfying the inclusion criteria
- Subjects that develop withdrawal criteria whilst on the study but are not withdrawn
- Subjects that receive the wrong treatment or an incorrect dose

- Subjects that receive an excluded concomitant medication
- Vomiting following oral dosing (each instance will be discussed in the CSR)
- Deviation from GCP
- Sample processing errors that may lead to inaccurate bioanalytical results
- Failure to fast (in fasted arm) or incomplete meal consumption (in fed arm) prior to dosing

The following deviations will be identified and confirmed prior to or at the Data Review Meeting at the latest. Important protocol deviations include:

- Deviations from the inclusion and exclusion criteria
- Deviations post inclusion

A data review meeting will be held to discuss and update the definition of important protocol deviations so as to determine the evaluability of the subjects prior to database lock.

All important protocol deviations should be documented in CDISC datasets whether identified through sites monitoring or medical review. Please refer to Protocol Deviation Guide for more details.

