10.2 Definition of Analysis Sets and Subgroups

Screening Population

The Screening population includes all subjects who have signed the main informed consent (i.e., screening failures plus subjects enrolled).

Randomized Population

The Randomized population includes all randomized subjects.

Safety Population

The Safety Population includes all subjects who received at least 1 dose of IMP. In general, clinical data will be analyzed for the Safety Population.

Pharmacokinetic Population

The PK Population includes all participants who completed the study with adequate study medication compliance ([Section 15](#)), without any relevant protocol violations or events with respect to factors likely to affect the comparability of PK results, and with sufficient evaluable data to determine primary endpoints ($AUC_{0 \rightarrow t}$ and C_{max}) for both treatments. If participants receive concomitant medication that potentially affects PK for the treatment of an AE, their inclusion in the PK Population will be decided on a case-by-case basis. Emesis occurring within 2 times of the median t_{max} for a given treatment will be considered a relevant event likely to affect the comparability of PK results. Similarly, a predose concentration for a given treatment period which

exceeds 5% of C_{max} will be considered a relevant event affecting PK results. All PK analyses will be based on the PK Population. Data for subjects excluded from the PK Population will be included in listings.

11

General Specifications for Statistical Analyses

11.1

Output Presentations

The shells provided with this SAP describe presentations for this study and therefore the format and content of the summary tables, listings and figures to be provided by PPD. Unless otherwise indicated all analyses will be presented separately for the two treatments (Treatment A and Treatment B) and/ or for two treatment sequences (Sequence A-B and Sequence B-A) under different food consumption condition (fed and fasted).

11.2

Listings

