16.1 Primary Endpoint Analyses

The primary endpoints are the following PK parameters calculated from metformin plasma concentrations under fasting or fed condition:

C_{\max} of metformin

$AUC_{0 \rightarrow t}$ of metformin

The null and alternative hypotheses are the following:

$H_0 : \text{for } AUC_{0 \rightarrow t} \ \mu_T / \mu_C \leq 0.8 \text{ or } \mu_T / \mu_C \geq 1.25$, for at least 1 primary endpoint
 $\text{for } C_{\max} \ \mu_T / \mu_C \leq 0.8 \text{ or } \mu_T / \mu_C \geq 1.25$

$H_1 : \text{for } AUC_{0 \rightarrow t} \ 0.8 < \mu_T / \mu_C < 1.25$, for both primary endpoints and for both fasting and
 $\text{for } C_{\max} \ 0.8 < \mu_T / \mu_C < 1.25$
fed groups

where μ_T and μ_C are the means of primary endpoints following test IMP and reference IMP (Treatment A and Treatment B), respectively.

The analysis of primary endpoints will be based on PK Population.

The primary endpoints, C_{max} and $AUC_{0 \rightarrow t}$ in fasting and fed group, will be log-transformed and a mixed-effects model will be applied. The model will include fixed effects for sequence, treatment, and period and a random effect of subject nested within sequence. Treatment differences on the log scale will be estimated for the parameters together with their 90% CIs. The least squares mean together with their 95% CIs by treatment will also be estimated. Point estimates and CIs will be back-transformed to the original scale for presentation, i.e., ratios of geometric means and corresponding 90% CIs for Treatment A/Treatment B, and geometric means and corresponding 95% CIs by treatment, respectively. Intra-subject CV estimated from the model will also be presented. Bioequivalence will be assessed separately in the fed and in the fasted group, and the trial will be considered successful only if BE is established for both primary parameters in both groups. The BE will be considered established if the 90% CIs for the ratios of geometric means between the investigational product and the comparator fall within 80.00% to 125.00% for all these comparisons.

The following example code could be used:

```
proc mixed data=pkparam;
  by foodconsumption param;
  class sequence period trt subjid;
  model lnest = sequence period trt /ddf=kr;
  random subjid(sequence);
  estimate 'A vs B' trt 1 -1 /alpha=0.1 cl;
  lsmeans trt /alpha=0.05 cl;

run;
```

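### Does SAP 16.3.2 apply a different exclusion rule for high predose concentrations from the PK Population definition, and does the plan leave other exclusions open to bias?

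*SAP*

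**What the plan says.** **Population level.** Protocol 9.3 and SAP 10.2 admit to the PK Population participants who have no relevant violation or event and have enough data to determine AUC0-t and Cmax under both treatments. In both documents a predose value above 5% of that period's Cmax "will be considered a relevant event affecting PK results".

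**Profile level.** SAP 16.3.2 covers noncompartmental estimation. It keeps a profile with such a predose value in the calculation, then states that "the corresponding derived PK parameters will be excluded from summaries and inferential statistics as appropriate", with the handling reported in the CSR. It does not mention the participant's other period and does not cite SAP 10.2.

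**Which data enter inference.** SAP 16.1 bases the primary analysis on the PK Population. SAP 16.3.1 is general: "All statistical analyses and descriptive summaries of PK data will be performed on the PK Population". The primary model has "a random effect of subject nested within sequence".

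**Who decides, and when.** Protocol 9.3: "The final decision to exclude participants from any analysis population will be made prior to database lock". For participants given a medication for an AE that may affect PK, "their inclusion in the PK Population will be decided on a case-by-case basis". SAP 10.1 adds: "A data review meeting will be held to discuss and update the definition of important protocol deviations so as to determine the evaluability" of subjects before lock. SAP 16.3.1 sets a limit: "Any other PK concentrations that appear implausible to the Pharmacokineticist must not be excluded from the analysis".

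**The concern.** There are two worries.

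First, the unit of exclusion. The population definition works on participants and the 16.3.2 sentence works on profiles. A model with a random subject effect accepts a participant with one period only, and gives no warning. An analyst who took 16.3.2 alone could drop the affected profile and keep its companion, while a colleague following 10.2 would drop both. SAP 16.3.2 also says parameters are calculated for all volunteers with sufficient data and, further on, for each subject in the PK Population. The PK Population is the only set behind the four primary 90% confidence intervals (two parameters, two food groups), all of which must pass. The fed group has only 16 participants and is not topped up until it falls below 12.

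Second, discretion. The trial is open-label, concomitant-medication cases are judged singly, and the data review meeting may revise what counts as an important deviation. Neither document says whether those deciding can see concentrations. If they could, and let the results guide them, the type I error of the bioequivalence test would rise above 5%.

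**Working it through.** **1. Setting the passages side by side**

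| Question | Text | Answer |
|---|---|---|
| Is the profile calculated? | SAP 16.3.2 | Yes |
| Do its parameters enter summaries or inference? | SAP 16.3.2 | No |
| Is the participant in the PK Population? | Protocol 9.3, SAP 10.2 | No: relevant event |
| Can inference use someone outside that population? | SAP 16.1, 16.3.1 | No |
| What happens to the other period's data? | SAP 10.2, Protocol 9.4.4 | Listed and annotated, not summarised |

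No row contradicts another. The sentence in 16.3.2 never says that only the affected profile goes or that the other one stays. The last row also settles who gets parameters: they are calculated and listed for everyone with data, and summarised for the PK Population. With both periods present for every participant analysed, the mixed model estimates the treatment effect from within-participant differences alone, so the random effect adds no unpaired information.

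**2. How often the event could arise from carryover**

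The washout is 7 days = 168 h. Residual drug above 5% (1/20) of Cmax needs a half-life of at least 168 / log2(20) = 168 / 4.32 = 38.9 h. The guideline rule quoted in Protocol 6.3.1 asks for at least 7 half-lives. A washout that meets it implies a half-life of at most 168 / 7 = 24 h and leaves at most 2^-7 = 0.78%. So the trigger should be rare.

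**3. What it would cost if the companion record were kept anyway**

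The CVs and assumed ratio are redacted, so all values here are assumptions. For complete pairs, SE = σw × √[½(1/n1 + 1/n2)], with σw = √ln(1 + CVw²).

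Example: fed group of 16, CVw 20%, between-subject CV 20%.
- σw = √ln(1.04) = 0.198.
- Participant removed (7 and 8 left): SE = 0.198 × √[½(1/7 + 1/8)] = 0.198 × 0.366 = 0.0725.
- Profile only removed, generalised least squares: SE = 0.0719, a ratio of 0.992.
- The 90% CI multiplies and divides the estimate by exp(t × SE), with 13 df: 1.137 against 1.136.

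Over CVw 10–30% and between-subject CV 20–40%, the SE ratio is 0.984–0.999 for fed n = 12–16 and 0.994–1.000 for fasting n = 28–38.

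Two simulations, each given one affected profile and judging one parameter, used REML with t on n−3 df in place of Kenward-Roger:

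| Setting | Shift in ratio | Verdict differs |
|---|---|---|
| n = 16/38 (10,000 trials per setting) | mean 0.2–0.7 points | 0–4.3% |
| n = 12/28 (same) | mean 0.3–0.9 points | 0.3–6.4% |
| Fed n = 12–16, CVw 15–25%, ratio 0.95 (1,500 trials) | median 0.3–1.0% | 1.6–7.4% |

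The first two rows assume CVw 15–20% fed and 20–25% fasting, between-subject CV 25–30%, and a true ratio of 0.92–1.00. The third assumes a between-subject CV of 25%. Differing verdicts fall in both directions. In the third row the pass rates under the two rules differ by about 1 point at most, for example 77.8% against 78.9% at n = 12 and CVw 15%. In the first two rows the pass rate with the participant removed is lower by at most 0.7 points (n = 16/38) or 1.8 points (n = 12/28).

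**4. Discretion**

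With a true ratio of 1.25 and 40,000 trials per setting, type I error per parameter is:
- no one removed: 4.7–5.1%;
- one participant removed regardless of result: 4.8–5.2%;
- one flagged participant kept or dropped with knowledge of the result: 5.3–6.5%;
- two such participants: 6.0–8.0%;
- the participant with the highest test/reference ratio removed on purpose: 10.6–14.6%.

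Inflation therefore needs a decider who knows the bioequivalence result. The last line is a bound on misconduct that no text permits.

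**The case for a change.** The strongest case for a change is that, if 10.2 already removes the participant, the exclusion in 16.3.2 is redundant and its closing qualifier has nothing to decide. A reader who wants each sentence to do some work is pushed towards the profile-level rule. The model would run on such data, and the choice would come to light only in the CSR. That is a fair criticism of the drafting. It does not outweigh two explicit statements that inference runs on the PK Population, together with a definition requiring both treatments. The sentence still has a use in the estimation section, where it tells the pharmacokineticist to calculate the profile and keep it out of the summaries.

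On discretion, it is true that deciding before lock is not the same as deciding without sight of concentrations, and that the ban on dropping implausible values covers concentrations, not participants' evaluability. But the scope is small. Protocol 6.5 withdraws anyone who takes a prohibited medication, and 6.5.1 permits only limited paracetamol and hormonal contraception, apart from an emergency clause. Protocol 9.4.1 holds the analysis until data checks and assessments are complete. SAP 10.1 refers to a separate Protocol Deviation Guide, not available here, which may cover access. The predose rule cannot be applied without concentrations. A strict blind on exclusions would also have to leave room for those made because primary endpoints cannot be determined (SAP 10.2) or fewer than three valid postdose points exist (SAP 16.3.2).

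**Conclusion.** The plan followed as written gives a sound result: a participant with a predose value above 5% of Cmax is outside the PK Population, both profiles are listed, and neither enters inference. SAP 16.3.2 lacks a cross-reference to 10.2, a gap that analysts can fill from 10.2, 16.1 and 16.3.1. Even under the other reading, and given one event that should be rare, the ratio moves by under one point on average and a single-parameter verdict changes in at most about 7% of simulated trials, under the assumed CVs.

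The silence on access to concentrations is an unstated policy and contradicts nothing in the documents. Stating it would be good practice. No gain is shown, because removing a participant without regard to the result leaves type I error at about 5%, and the higher figures assume knowledge of the outcome. Both conclusions rest on the two public documents alone. The wording does not call for a change to the plan.

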6.3.2 Blinding

Not applicable as this is an open label study.

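### Does the SAP need a written sampling-coverage rule before an incomplete profile may count for the primary AUC0-t and Cmax?

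*SAP*

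**What the plan says.** SAP 16.3.2 sets three quality conditions on the terminal phase. Failing the Rsq condition (at least 0.800) or the span condition (at least two half-lives) leads to a flag. Exceeding 20.0% for AUCextra%, a limit introduced by "To ensure a reliable estimate of the extent of exposure in pivotal trials (e.g., BE", means that AUC0-inf, AUCextra%, lambda-z, half-life, Vz/f and CL/f "will not be included in the calculation of descriptive statistics or statistical analyses". AUC0-t and Cmax are not on that list.

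Entry to the primary model is through the PK Population (Protocol 9.3, SAP 10.2). It requires completion of the study, no relevant violation or event, and both treatments "with sufficient evaluable data to determine primary endpoints". The same paragraph gives thresholds for two events: vomiting ("Emesis occurring within 2 times of the median" tmax) and a predose value above 5% of Cmax. It gives none for missing samples, although SAP 16.3.1 foresees them: "Missing concentrations (e.g., no sample, insufficient sample volume for analysis, no result, or result not valid".

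One numerical minimum reaches the primary parameters. SAP 16.3.2 says "At least 3 valid, postdose concentration points will be required in the PK profile to obtain any PK parameter estimate", directly after a sentence about volunteers with sufficient concentration-time data.

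On procedure, SAP 10.1 says "A data review meeting will be held to discuss and update the definition of important protocol deviations" and that this settles evaluability before lock. It refers to a Protocol Deviation Guide for further detail. Blinding is "Not applicable as this is an open label study" (Protocol 6.3.2).

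**The concern.** A rule whose stated aim is a reliable extent of exposure in a bioequivalence trial does not touch the primary extent measure. AUC0-t ends at the last quantifiable sample, so losing late samples in one period shortens it for one product only. A shortened test profile lowers the test/reference ratio and could hide a true excess; a shortened reference profile does the reverse.

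Whether to keep such a profile is then a judgement made open-label, by a meeting that may revise the definition of important deviations. Concentrations are probably in hand by then: the predose rule needs Cmax, the vomiting rule needs the median tmax, and no passage withholds the data. In a fed group of 16, one kept or dropped profile might change the verdict. Read literally, the three-point floor would admit a profile with almost no coverage.

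**Working it through.** The documents give no figure to reproduce: the CVs from the earlier study are blacked out and no kinetic parameters are stated. CVs and kinetics below are assumptions.

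**1. The literal floor.** Protocol 8.5 plans 17 samples per period, 16 of them postdose, so the floor is 3/16 = 18.75%. Take constant-rate input to a tmax of 4, 5 or 7 h, then a half-life of 4, 6 or 8 h. Samples at 0.5, 1 and 2 h alone would give 2-8% of AUC0-t and still meet the floor. Read alone, it is not a coverage rule.

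**2. How much AUC0-t is lost.** Six one-compartment profiles (ka/ke 0.5/0.11, 0.35/0.17, 0.25/0.12, 0.2/0.15, 0.3/0.10, 0.25/0.20; tmax 3.9-5.8 h, half-life 3.5-6.9 h), linear-up/log-down on the protocol times, lambda-z from the last three points:

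| Last sample | Share of AUC0-48 | AUCextra% |
|---|---|---|
| 24 h | 88-97% | 3-14% |
| 14 h | 65-83% | 19-41% |
| 8-10 h | 38-67% | 39-84% |

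A substantial loss needs the 24, 30, 36 and 48 h samples all missing in the same period.

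**3. Effect on the ratio and interval.** If one participant's test AUC is multiplied by f, the geometric mean ratio in a balanced group of n is multiplied by f^(1/n).
- n = 16: 0.80^(1/16) = 0.986; 0.65^(1/16) = 0.973; 0.50^(1/16) = 0.958.
- n = 38: 0.50^(1/38) = 0.982.

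For n = 16, CV 15% and true ratio 1.00, s = sqrt(ln(1 + 0.15²)) = 0.149. The expected 90% CI is exp(±1.761 × 0.149 × sqrt(2/16)) = 91.1-109.7%. With one test profile at f = 0.50, the variance of the within-participant log differences becomes 2s² + (ln f)²(1 − 2/n)/(n − 2) = 0.0445 + 0.0300 = 0.0745. The interval is then exp(−0.0433 ± 1.761 × sqrt(0.0745/16)) = 84.9-108.0%, still inside the limits.

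**4. Probability of passing on AUC0-t.** Simulated 2×2 crossovers, sequence- and period-adjusted 90% CI against 80.00-125.00%, n = 16, CV 15%, one short test profile:

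| f | True ratio 1.00: complete → kept | Keep/drop verdicts differ | True ratio 0.95: complete → kept | Keep/drop verdicts differ |
|---|---|---|---|---|
| 0.80 | 98% → 97% | 2% | 93% → 87% | 6% |
| 0.65 | 98% → 95% | 4% | 93% → 78% | 14% |
| 0.50 | 98% → 86% | 13% | 93% → 57% | 34% |

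Dropping the participant instead gives 97% and 91%. The result depends on the assumed CV. At true ratio 1.00 and f = 0.65, the pass probability goes from 100% to 99.9% at CV 10%, and from 83% to 76% at CV 20%. For the fasting group (n = 38, CV 20%, true ratio 0.95), 98% becomes 96% (f = 0.65) or 94% (f = 0.50).

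**5. False passes.** At a true ratio of 1.25, n = 16 and CV 10-20%, keeping a profile at f = 0.65 or 0.50 raises the AUC pass rate from 5% to roughly 8-9%. This is for one parameter in one group, given that such a profile exists. Trial success needs both parameters in both groups (SAP 16.1).

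**6. Could the 20.0% limit serve as the missing rule?** Not well. It would pass one of the six 14 h truncations (19.1%). It also cannot see a missed peak: under the profiles of step 1, losing the 4-8 h samples cuts observed Cmax to 59-81% while AUCextra% stays at 2% or less.

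**7. What already limits the scenario.**
- Participants are inpatients from Day -1 to Day 10 (Protocol Table 1, note a), so the 48 h sample of each period is drawn on the unit.
- Withdrawal in Period 1 leaves no data on the second treatment, so SAP 10.2 excludes the participant.
- Withdrawal in Period 2 conflicts with the completion condition, and an extra PK sample is drawn at withdrawal.
- SAP 16.3.1 lets a concentration be left out only for a protocol deviation, a documented handling error or an analytical error, agreed before analysis and explained in the report. Values that merely look implausible stay in.
- Exclusions from analysis populations are decided before lock (Protocol 9.3).

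**The case for a change.** The best case for a change is that these safeguards set a time, not a threshold. Deciding before lock is not deciding before concentrations are seen, and in an open-label trial the direction of each choice is predictable. Nor is the completion condition watertight: Protocol 4.4 lists a premature withdrawal visit among the final visits of a completer, whereas SAP 12.1 counts completers and early terminations separately. A coverage rule would cost one sentence.

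Much of this stands. The term is undefined, three points is a weak floor, and a short test profile in the fed group matters if it occurs. What does not follow is that the plan leads to a wrong analysis. The 20.0% limit concerns extrapolation with lambda-z, which AUC0-t does not use, so confining its effect to lambda-z parameters is coherent. The list of important deviations is expressly not exhaustive and includes sample processing errors. It also defers to a guide not available here, so the absence of a sampling rule from the SAP does not show that none exists. Any threshold would be the sponsor's choice, since the documents provide nothing from which to derive one.

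The two predose wordings are compatible: SAP 10.2 removes the participant from the PK analyses, and SAP 16.3.2 says how the affected profile is calculated, listed and left out of summaries.

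**Conclusion.** No change is needed. The SAP leaves a term undefined, and a pharmacokineticist and statistician at the pre-lock review would fill it sensibly: a period without any sample from 24 h onward would be questioned under the sufficiency and comparability conditions whether or not a number is written down. It would be wrong to say that no written criterion exists, because the three-point minimum reaches AUC0-t and Cmax. It is fair to call that minimum weak. A sentence on coverage around the peak and in the tail would be a reasonable courtesy to the reader, but it corrects no rule shown to give a wrong result.

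The effect is small unless nearly all late samples are lost in one period: a last sample at 24 h costs 3-12% of one participant's AUC0-t. In the severe cases (f = 0.65 or 0.50, fed n = 16, CV 15%, true ratio 0.95) keeping or dropping the profile changes the AUC verdict in 14% or 34% of simulated trials. These figures assume that the event has happened, and they rest on assumed CVs and one-compartment kinetics. The documents do not say how often it would happen; the inpatient design suggests seldom. If the true CV were well above 15%, the fed group would be more sensitive, but it would also be short of power with complete profiles (83% on AUC at CV 20% and true ratio 1.00).
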